7.5.1. Prior Therapies

All prior therapies used in the treatment of any of the tumor types under study will be collected from patients, including drug name, start and stop dates and treatment response. Data will be summarized in tables and presented in the listings. Descriptive statistics will be used to assess the impact of prior treatments on the efficacy endpoints.

7.6. Statistical Analysis Methodology

Data will be summarized and/or analyzed by cohort. Safety and demographic data will be summarized using standard tabulations and listings. Continuous variables will be summarized using descriptive statistics such as mean, standard deviation, median, minimum value, and maximum value. Continuous variables may be summarized by a clinically relevant discretization, as appropriate. Categorical variables will be summarized using frequency counts and percentages. Time-to-event data will be summarized using the Kaplan-Meier method. Where appropriate, 95% confidence intervals around point estimates will be presented, and estimates of the median and other quantiles, as well as individual time points (e.g., 3-month, 6-month, and 12-month rates), will be produced. Data will be provided in data listings.

Details of the statistical analyses, methods, and data conventions are described in the SAP.

7.6.1. Analysis of Primary Efficacy Endpoint

For each tumor-specific cohort, a Bayesian approach with non-informative Jeffreys prior beta distribution with parameters $a = 0.5$ and $b = 0.5$ will be used to estimate the ORR and its 95% credible interval based on the posterior distribution.

At the time of analysis, within each tumor-specific cohort, the prior distribution will be updated with all available data to obtain the posterior distribution of the true ORR. The posterior probabilities that ORR exceeds TV and LRV will be reported for each cohort. A high posterior probability that $ORR > LRV$ will support a “Go” decision to continue development in the cohort, and a low posterior probability that $ORR > TV$ will support a “Stop” decision to halt development in the cohort. A “Consider” decision results if neither a Stop nor a Go decision can be made. The specific criteria for making a Stop, Consider, or Go decision within each tumor-specific cohort are derived using the following acceptable risks:

- 10% false stop risk: maximum acceptable probability that $ORR > TV$ given that a Stop decision is made.

- 20% false go risk: maximum acceptable probability that $ORR \leq LRV$ given that a Go decision is made

Before reaching the planned sample size in a cohort, the posterior probabilities will be updated continuously after each patient or group of patients and will be used to determine, within each cohort, the predictive probability of eventually reaching a Stop decision at the planned sample size. If this predictive probability is $\geq 80\%$, then enrollment in that cohort may be stopped early for futility. Definitions of the decision boundaries can be found in [Section 7.6.6](#).

In general, Stop/Go and futility decision criteria are non-binding and may be regarded as guidance and information to be integrated with a full medical review of safety and efficacy data observed at the time of analysis in determining the next course of action.

No tests of statistical significance are planned.

Patients with missing ORR will be conservatively classified as non-responders for the primary analysis.

7.6.2. Analysis of Secondary Efficacy Endpoints

Secondary endpoints will be summarized by cohort using descriptive statistics. No formal tests of hypotheses are planned. Duration of response (DOR) and TTR will be evaluated using Kaplan-Meier estimates and curves will be generated based on these estimates.

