Given a sample size of 20 patients in SCLC group, where TV = 40% and LRV = 30%, the decision criteria are as follows: Go if ≥ 8 responses observed (40%); Stop if ≤ 5 responses observed (20%). With these criteria, there is a 58% probability of a Go decision and 13% probability of a Stop decision if the true ORR is 40%, and there is a 23% probability of a Go decision and 42% probability of a Stop decision if the true ORR is 30%.

TNBC

Given a sample size of 15 patients in the triple negative breast cancer group, where TV=25% and LRV=15%, the decision

criteria are as follows: Go if ≥ 4 responses observed (27%); Stop if ≤ 1 responses observed (7%). With these criteria, there is a 54% probability of a Go decision and 8% probability of a Stop decision if the true ORR is 25%, and there is a 18% probability of a Go decision and 32% probability of a Stop decision if the true ORR is 15%.

AML

The same sample size, TV, LRV, decision criteria, and probability statements as the TNBC group apply.

General Considerations

Data will be summarized and/or analyzed by cohort. Safety and demographic data will be summarized using standard tabulations and listings. Continuous variables will be summarized using descriptive statistics such as mean, standard deviation, median, minimum value, and maximum value. Continuous variables may be summarized by a clinically relevant discretization, as appropriate. Categorical variables will be summarized using frequency counts and percentages. Time-to-event data will be summarized using the Kaplan-Meier method. All time to event endpoints are measured from day of enrollment (Day-2 pretreatment baseline visit). Where appropriate, 95% confidence intervals around point estimates will be presented, and estimates of the median and other quantiles, as well as individual time points (e.g., 3-month, 6-month, and 12-month rates), will be produced. Data will be provided in data listings.

Objective response rate will be reported with category counts, percentage and 95% confidence interval. Duration of response (DOR), TTR, and OS will be evaluated using Kaplan-Meier estimates and curves will be generated based on these estimates.

SELLAS Life Sciences Group

Protocol: SLS17-201/MK3475-770 Protocol v1.1 (Amendment 1.0)

Galinpepimut-S

12 April 2019

Date of Protocol 12 April 2019
Amendment:

List of Abbreviations

Abbreviation	Definition
aa	amino acids
AE	adverse event

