6.8.2. Tumor Imaging During the Study

For solid tumors only, the first on-study imaging assessment should be performed at Week 9 (Day 1 \pm 7 days) from the date of enrollment. Subsequent tumor imaging should be performed at Weeks 18, 27, 36, 45, 54, 63, 72, and 84 (Day 1 \pm 7 days) or more frequently if clinically indicated. Imaging timing should follow calendar days and should not be adjusted for delays in cycle starts. Imaging should continue to be performed until disease progression is identified by the investigator.

Objective response should be confirmed by a repeat imaging assessment. Tumor imaging to confirm PR or CR should be performed at least 4 weeks after the first indication of a response is observed. Patients will then return to regular scheduled imaging, starting with the next scheduled imaging time point. Patients who receive additional imaging for confirmation do not need to undergo the next scheduled tumor imaging if it is less than 4 weeks later; tumor imaging may resume at the subsequent scheduled imaging time point.

Per iRECIST ([Section 6.8.5](#)), disease progression should be confirmed by the site 4 to 8 weeks after.

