7.2. Secondary Efficacy Endpoints

The secondary efficacy endpoints are TTR, time to next treatment and DOR.

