7.5. Analysis Sets

- The full analysis set (FAS) comprises all patients who are assigned to receive study treatment as per the ITT principle, regardless of whether or not they subsequently go on to receive study treatment or whether they deviate from the protocol in any major way.

- The modified intent-to-treat (mITT) set comprises all patients who are assigned to receive study treatment and have at least 1 post-baseline efficacy assessment (RECIST 1.1), even if they deviate from the protocol in any major way. The mITT will also include any patient that goes off study treatment because of clinical progression prior to the first scheduled per-protocol scan.
- The safety analysis set comprises all patients who receive any amount of study drug.
- The per-protocol set (PPS) comprises all patients who are assigned to receive study treatment, receive at least 1 injection of study treatment, have at least 1 post-baseline efficacy assessment (RECIST 1.1), and do not deviate from the protocol in any major way.

All efficacy analyses will be based on the FAS and will be conducted on the mITT set and PPS populations for exploratory purposes. For CRC patients, only those with MSS and MSI-L will be included in the efficacy primary analysis. The safety analyses will be based on the safety analysis set and will group patients according to treatment actually received. Secondary and exploratory efficacy analyses will be performed on the ITT/FAS as well as on the mITT and PPS populations for exploratory purposes.

Major protocol deviations will be defined in more detail in the study statistical analysis plan (SAP), and may include, but not be limited to, incorrect diagnosis and poor compliance.

All analyses using the PPS will group patients according to treatment actually received.

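### Time to response is to be analysed by Kaplan-Meier with no stated rule for progression or death before response; if those patients are censored at that event, the curve overstates the probability of response

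*Combined protocol and SAP*

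**What the plan says.** TTR is one of three secondary efficacy endpoints. Section 7.2: "The secondary efficacy endpoints are TTR, time to next treatment and DOR". Section 7.6.2 gives the method: "Duration of response (DOR) and TTR will be evaluated using Kaplan-Meier estimates and curves will be generated based on these estimates". The Synopsis (General Considerations) repeats it and adds OS: "Duration of response (DOR), TTR, and OS will be evaluated using Kaplan-Meier estimates".

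The surrounding text sets the frame:

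- Population, Section 7.5: "Secondary and exploratory efficacy analyses will be performed on the ITT/FAS as well as on the mITT and PPS populations for exploratory purposes".
- Time origin, Synopsis: "All time to event endpoints are measured from day of enrollment (Day-2 pretreatment baseline visit").
- Output, Section 7.6: where appropriate, medians, other quantiles and "individual time points (e.g., 3-month, 6-month, and 12-month rates), will be produced".
- The ORR, by contrast, keeps every non-responder in the denominator. Section 7.6.1: "Patients with missing ORR will be conservatively classified as non-responders for the primary analysis".

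The document does not define the TTR event, does not limit TTR to responders, does not say what happens to a patient who progresses or dies first, and does not mention competing events or cumulative incidence. The only explicit censoring rule, in Section 7.7.1, is for OS. The same section promises imputation for missing secondary-endpoint data without naming a method. Section 7.6 leaves data conventions to the SAP, and no SAP text beyond Section 7 is in the combined document.

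**The concern.** Kaplan-Meier treats a censored patient as someone who would have gone on to respond at the same rate as the patients still at risk. That is reasonable for a patient lost to follow-up or cut off administratively. It is not reasonable for a patient who has died, and it is doubtful for one whose disease has progressed. If such patients are censored, each later response is divided by a risk set from which the failures have been removed, and the curve climbs above the proportion who actually respond.

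TTR matters because the Synopsis names it among the measures on which the combination might improve on pembrolizumab alone. Section 7.4 also says that a cohort landing between Stop and Go will be judged partly on secondary endpoints, and that secondary-endpoint data may prompt enrolment of about 10 more patients. A curve that appears to show more response than the ORR could mislead in just those borderline cohorts.

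**Working it through.** **1. The plan's own figures.** No numerical TTR value is stated, so the check starts with the ORR design tables. With X binomial, P(Go) = P(X ≥ 4) and P(Stop) = P(X ≤ 1) for n = 20 and ORR 20% give 58.9% and 6.9%, leaving 34.2% for Consider. Table 11 prints 59, 34 and 7. All 27 cells of Tables 11 to 13 reproduce to rounding. Across them, Consider has probability 29% to 50%, which is how often secondary endpoints could come into play at the tabulated response rates.

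**2. Where censoring would fall.** The first scan is at Week 9, and Section 6.8.2 continues: "Subsequent tumor imaging should be performed at Weeks 18, 27, 36, 45, 54, 63, 72, and 84". Scanning runs until the investigator identifies progression. Under Section 6.8.3, when treatment stops for documented progression, the scan at discontinuation is the last one required if iRECIST is not used. Section 6.1.5 says that after the relapse and end-of-treatment procedures only adverse events and survival are followed. Response data therefore largely end at progression or death, and censoring at the last assessment puts the censoring time there.

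**3. Hand example (assumed timings).** n = 20. Week 9: 2 responses, 10 progressions. At risk at Week 18: 20 - 2 - 10 = 8. Week 18: 2 responses, 5 progressions.

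- 1-KM = 1 - (18/20)(6/8) = 1 - 0.675 = 32.5%.
- ORR = 4/20 = 20%. With progression as a competing event and complete follow-up, the cumulative incidence is also 20%.

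**4. Examples at each cohort's Go boundary (assumed timings, response counted before censoring at the same visit).**

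- CRC/OvC, 4/20, one response at each of Weeks 9, 18, 27 and 36, with 20, 13, 7 and 3 at risk: 1 - (19/20)(12/13)(6/7)(2/3) = 49.9%, against 20.0%.
- SCLC, 8/20, with 3, 3, 1 and 1 responses among 20, 12, 5 and 3 at risk: 1 - (17/20)(9/12)(4/5)(2/3) = 66.0%, against 40.0%.
- TNBC/AML, 4/15, with 1, 2 and 1 responses among 15, 10 and 5 at risk: 1 - (14/15)(8/10)(4/5) = 40.3%, against 26.7%.

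**5. Range.** The documents give no progression or death rate, so the median time m to progression or death without response was assumed to be 9, 18 or 36 weeks. The hazard of progression or death was h_p = ln 2/m. The response hazard h_r was solved from h_r/(h_r + h_p) × [1 - exp(-84(h_r + h_p))] = true ORR. Events were recorded at the next scheduled scan, with 3,000 simulated trials per setting. The imaging weeks were also used for AML, as a simplification. Cells show mean 1-KM at Week 84 / mean observed ORR, in percent, with the share of trials in which the curve ended above the ORR.

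| Setting | m = 9 | m = 18 | m = 36 |
|---|---|---|---|
| n = 20, ORR 10% | 24.6 / 10.0 (60%) | 24.5 / 10.0 (75%) | 18.3 / 10.1 (81%) |
| n = 20, ORR 20% | 43.9 / 20.0 (82%) | 45.7 / 20.1 (94%) | 35.6 / 20.3 (96%) |
| n = 15, ORR 25% | 48.9 / 25.1 (78%) | 52.0 / 25.0 (92%) | 43.1 / 25.1 (95%) |
| n = 20, ORR 40% | 69.2 / 39.8 (93%) | 73.8 / 40.2 (99%) | 65.7 / 39.8 (100%) |

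The smallest mean excess is 18.3 - 10.1 = 8.2 points and the largest is 73.8 - 40.2 = 33.6 points.

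**6. Other readings.** If non-responders are instead censored at the maximum follow-up time, 1-KM equals the ORR. If only responders are analysed, the last patient at risk is a responder, so the curve reaches 100% whatever the ORR.

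**The case against.** The strongest reply is that the plan never says patients are censored at progression or death. DOR shares the sentence with TTR and can exist only for responders, so TTR may be meant for responders too. The general full-analysis-set statement covers DOR as well and so does not settle the matter. Among responders nobody is censored for progression, and the Kaplan-Meier median is essentially the ordinary median. Censoring at maximum follow-up would also remove the bias, and the SAP may state a rule. Section 7.6.2 also opens by promising descriptive summaries, and Section 7.6 lists median, minimum and maximum among them, so part of the remedy is arguably planned. No tests are planned, and the decision criteria are non-binding.

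Much of this stands, and it limits the point to a conditional one. It does not remove it: neither bias-free reading is written down, the follow-up rules lead towards censoring at progression, and a responder-only curve carries no information about how likely response is.

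Several stronger readings are tempting, but the documents do not support them:

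- That patients who progress can no longer respond. This is certain only for death. Section 6.8.5 allows treatment past first radiologic progression and accepts that response can follow a flare. RECIST 1.1 remains the primary measure and iRECIST response is exploratory, so this softens the claim without rescuing Kaplan-Meier.
- That response rates of 10% to 40% are expected, so most patients will progress or die unresponsive. Those figures are the LRV and TV decision thresholds, and no progression rates are given.
- That the curve contradicts the primary result. The ORR is estimated and reported separately; 1-KM misleads only if read as a response rate.
- That the 20% ORR cohort in step 3 could show a 100% curve. That needs a later response in the one patient still at risk, which makes the ORR 5/20 = 25%.

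**Conclusion.** The point holds as an under-specified and poorly chosen summary for TTR, not as a stated error in handling censored patients. If TTR is analysed in the full analysis set with censoring at progression or death, 1-KM overstates the probability of response: 32.5% against 20% in the hand example, and on average about 8 to 34 points too high in the simulated settings, ending above the observed ORR in 60% to about 100% of trials. These sizes rest on assumed event timings and constant hazards; the direction does not depend on the particular values, provided responses occur after such censoring has begun. The consequence is confined to a descriptive secondary endpoint that may colour a Consider or expansion decision. The ORR, the Go/Stop boundaries, the futility rules and Tables 11 to 13 do not change.

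**What to change.** In Section 7.6.2 and the Synopsis, replace Kaplan-Meier for TTR with:

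- (a) the median and range of TTR among responders, labelled as responders only; and
- (b) if a cohort-level curve is wanted, the cumulative incidence of RECIST 1.1 response (CR/CRi/CRp in AML) in the full analysis set, with death, progression and new anticancer therapy before response as competing events. Patients still event-free are censored at their last assessment.

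With complete follow-up, curve (b) ends at the ORR for the same patients. Keep Kaplan-Meier for DOR and OS. The protocol already provides for recording response, progression, death and new anticancer therapy, so no new data are needed. The cost is slightly more SAP wording, a standard procedure and a less favourable-looking curve.

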7.6.3. Analyses of Exploratory Endpoint

Analysis of exploratory endpoints will be defined in the study SAP.

7.6.4. Safety Analyses

All safety analyses will be based on the safety analysis set. Specifically for safety, t-zero for all time measurements assumes the date of first GM-CSF administration (day -2 of the entire protocol schedule).

7.6.4.1. Adverse Events

Missing information regarding AEs will be imputed in a conservative manner. For example, a missing relatedness will be assumed to be certainly related; a missing severity will be assumed to be severe and so on.

All AEs will be coded using the latest version of MedDRA.

The severity of AEs will be coded using CTCAE v5.0.

All TEAEs will be summarized and presented in the listings by the number of patients reporting an event, the percentage of patients with that event, and the grade, duration, and relationship to treatment. Percentages will be based on the number of patients who received each treatment during the study. The incidence of SAEs, including death, and AEs leading to study treatment discontinuation will also be tabulated.

7.6.4.2. Laboratory Test Results

For all laboratory tests with continuous results, absolute value and change from baseline will be summarized by visit and treatment group. For laboratory tests with categorical results, shift from baseline will be summarized by visit and treatment group.

Shift tables for laboratory test results by severity will be produced and, for a subset of tests to be specified in the study SAP, separate shift tables indicating hyper- and hypodirectionality of change will be produced.

Shift tables for urine dipstick test results by grade may also be produced as appropriate.

Clinically significant laboratory test results will be flagged and listed. Reference ranges will be provided.

7.6.4.3. 12-Lead Electrocardiogram Results

Twelve-lead electrocardiogram (ECG) measurements will be recorded at the pretreatment screening visit. Each ECG will be classified as “abnormal” or “normal” and the relevance of the abnormality will be recorded as “clinically significant” or “not clinically significant.”

7.6.4.4. Physical Examination

Physical examinations will be performed at the pretreatment screening visit. Abnormal findings identified will be followed until resolution or stabilization. All ongoing findings will be recorded as pretreatment AEs and will be graded by CTCAE v5.0.

7.6.4.5. Vital Signs

Vital signs (body temperature [centigrade or Fahrenheit], systolic and diastolic blood pressure [BP], heart rate, and respiratory rate) and weight at each visit, plus height and weight at pretreatment screening for calculation of body mass index will be summarized over time in terms of absolute values and changes from baseline by visit and treatment group. For each parameter, a shift table comparing the baseline value to the maximum on-treatment value by treatment group will be presented.

7.6.4.6. Eastern Cooperative Group Performance Status

The ECOG performance status will be measured at each visit. The definition of each ECOG grade is presented in [Appendix 12.3 \(Oken et al, 1982\)](#). The ECOG data will be summarized by treatment group and visit.

7.6.5. Interim Analyses

Not applicable.

7.6.6. Go/No-Go and Futility Monitoring Guidelines

This study uses a Bayesian monitoring approach to guide decision-making using data on the primary efficacy endpoint (ORR) within each cohort. The specific criteria for making a Stop, Consider, or Go decision within each tumor-specific cohort at the planned sample size are derived using the following acceptable risks:

- 10% false stop risk: maximum acceptable probability that $ORR > TV$ given that a Stop decision is made.
- 20% false go risk: maximum acceptable probability that $ORR \leq LRV$ given that a Go decision is made

The Stop or Go decision criteria in each cohort are presented in Table 14.

Table 14 Decision Criteria for a Stop or Go Decision in Each Cohort at the Planned Sample Size

	Planned Sample Size	Target Value (TV)	Lower Reference Value (LRV)	Minimum Number of Responses for a Go Decision	Maximum Number of Responses for a Stop Decision
CRC	20	20%	10%	4	1
OvC	20	20%	10%	4	1
SCLC	20	40%	30%	8	5
TNBC	15	25%	15%	4	1
AML	15	25%	15%	4	1

AML = acute myeloid leukemia; CRC = colorectal cancer; ORR = overall response rate; OvC = ovarian cancer; LRV = lower reference value; SCLC = small cell lung cancer; TV = target value

Before reaching the planned sample size in a cohort, the posterior probabilities will be updated continuously after each patient or group of patients and will be used to determine, within each cohort, the predictive probability of a Stop decision at the planned sample size. If this predictive probability is $\geq 80\%$, then enrollment in that cohort may be stopped early for futility. The criteria for early futility stopping within each cohort are as follows:

CRC or OvC (N = number of patients currently enrolled in the cohort):

- If $N < 8$, there is insufficient data on ORR for a futility recommendation;
- If $N \geq 8$, futility stopping considered if no responses observed;
- If $N \geq 18$, futility stopping considered if ≤ 1 response observed.

SCLC (N = number of patients currently enrolled in the cohort):

- If $N < 3$, there is insufficient data on ORR for a futility recommendation;
- If $N \geq 3$, futility stopping considered if no responses observed;
- If $N \geq 7$, futility stopping considered if ≤ 1 response observed;
- If $N \geq 11$, futility stopping considered if ≤ 2 responses observed;
- If $N \geq 14$, futility stopping considered if ≤ 3 responses observed
- If $N \geq 17$, futility stopping considered if ≤ 4 responses observed

TNBC or AML:

- If $N < 6$, there is insufficient data on ORR for a futility recommendation;
- If $N \geq 6$, futility stopping considered if no responses observed;
- If $N \geq 13$: futility stopping considered if ≤ 1 response observed.

After reaching the planned sample size in a cohort, enrollment may be increased by approximately 10 additional patients in that cohort if the sponsor determines that further data on the primary or secondary endpoints is needed to clarify the efficacy signals for a Go/No-Go decision. In case additional patients are enrolled in a cohort, the decision boundaries for the expanded cohorts will be calculated using the same levels of acceptable risks used to

derive the initial boundaries, and futility monitoring will continue as before using $\geq 80\%$ predictive probability of a Stop decision as a threshold to recommend early futility stopping.

In general, Stop/Go and futility decision criteria are non-binding and may be regarded as guidance and information to be integrated with a full medical review of safety and efficacy data observed at the time of analysis in determining the next course of action.

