- The full analysis set (FAS) comprises all patients who are assigned to receive study treatment as per the intent-to-treat (ITT) principle, regardless of whether or

not they subsequently go on to receive study treatment or whether they deviate from the protocol in any major way.

- The modified intent-to-treat (mITT) set comprises all patients who are assigned to receive study treatment and have at least 1 post-baseline efficacy assessment (RECIST 1.1), even if they deviate from the protocol in any major way. The mITT will also include any patient that goes off study treatment because of clinical progression prior to the first scheduled per-protocol scan.
- The safety analysis set comprises all patients who receive any amount of study drug.
- The per-protocol set (PPS) comprises all patients who are assigned to receive study treatment, receive at least 1 injection of study treatment, have at least 1 post-baseline efficacy assessment (RECIST 1.1), and do not deviate from the protocol in any major way

All efficacy analyses will be based on the FAS and will also be conducted on the mITT set and PPS for exploratory purposes. The study's primary objective will be judged on the basis of the analysis of ORR. For CRC patients, only those with MSS and MSI-L will be included in the primary efficacy analysis. The safety analyses will be based on the safety analysis set and will group patients according to treatment actually received. Secondary and exploratory efficacy analyses will be performed on the FAS as well as on the mITT set and PPS for exploratory purposes.

Analysis of Primary Efficacy Endpoint: For each tumor-specific cohort, a Bayesian approach with non-informative

Jeffreys prior beta distribution with parameters $a = 0.5$ and $b = 0.5$ will be used to estimate the ORR (or CR/CRi/CRp rate in AML) and its 95% credible interval based on the posterior distribution.

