At the time of analysis, within each tumor-specific cohort, the prior distribution will be updated with all available data from the evaluable patients to obtain the posterior distribution of the true ORR. The posterior probabilities that ORR (or CR/CRi/CRp rate in AML) exceeds TV and LRV will be reported for each cohort. A high posterior probability that $ORR > LRV$ will support a “Go” decision to continue development in the cohort, and a low posterior probability that $ORR > TV$ will support a “Stop” decision to halt development in the cohort. A “Consider” decision results if neither a Stop nor a Go decision can be made. The specific criteria for making a Stop, Consider, or Go decision within each tumor-specific cohort are derived using the following acceptable risks:

- 10% false stop risk: maximum acceptable probability that $ORR > TV$ given that a Stop decision is made.
- 20% false go risk: maximum acceptable probability that $ORR \leq LRV$ given that a Go decision is made

Before reaching the planned sample size in a cohort, the posterior probabilities will be updated continuously after each patient (or group of patients) and will be used to determine, within each cohort, the predictive probability of eventually reaching a Stop decision at the planned sample size. If this predictive probability is $\geq 80\%$, then enrollment in that cohort may be stopped early for futility.

Stop/Go and futility decision criteria are non-binding and may be regarded as guidance and information to be integrated with a full medical review of safety and efficacy data observed at the time of analysis in determining the next course of action. No tests of statistical significance are planned.

CRC

Given a sample size of 20 patients in the CRC (third/fourth line) group, where TV = 20% and LRV = 10%, the decision criteria are as follows: Go if ≥ 4 responses observed (20%); Stop if ≤ 1 responses observed (5%). With these criteria, there is a 59% probability of a Go decision and 7% probability of a Stop decision if the true ORR is 20%, and there is a 13% probability of a Go decision and 39% probability of a Stop decision if the true ORR is 10%.

OvC

The same sample size, TV, LRV, decision criteria, and probability statements as the CRC group apply.

SCLC

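### Section 7.6.6 ties its futility cut-offs to enrolled patients, but at each cut-off the stated 80% criterion is met only if all N response outcomes are known

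*Combined protocol and SAP*

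**What the plan says.** Section 7.6.6 sets one criterion: if the predictive probability of ending in Stop at the planned sample size is 80% or more, enrollment may be stopped early. It then lists cut-offs by cohort, under the headings "CRC or OvC (N = number of patients currently enrolled in the cohort" and "SCLC (N = number of patients currently enrolled in the cohort". The TNBC/AML list uses N without defining it. If a cohort is expanded, "futility monitoring will continue as before using" the same 80% threshold. The section closes with "In general, Stop/Go and futility decision criteria are non-binding".

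The data behind the probability are described in two ways. The Synopsis (Analysis of Primary Efficacy Endpoint) says the prior is "updated with all available data from the evaluable patients", without defining evaluable. Section 7.6.1 says "updated with all available data to obtain the posterior distribution of the true ORR" and drops the word.

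Section 6.8.2 puts the first scan at Week 9 from enrollment and asks for confirmation of a response at least 4 weeks later.

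For CRC, entry is not restricted by microsatellite status. The Synopsis says "For CRC patients, only those with MSS and MSI-L will be included in the primary efficacy analysis", and Section 7.5 says "only those with MSS and MSI-L will be included in the efficacy primary analysis". Section 1.3.1.2.1 instead names MSS and MSI-H.

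**The concern.** A predictive probability can use only outcomes that have been observed. An enrolled count includes patients who have not yet had a scan. If the cut-offs were calculated on observed outcomes but are applied to enrolled patients, each pending patient is treated as a non-responder. The flag then appears earlier and more often than intended, and does not carry the 80% that the section attaches to it. Before any scan, the condition of no observed response is met automatically. SCLC is most exposed because its first cut-off is 3 patients.

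What is at stake is early closure of a cohort on very little evidence, in a trial whose purpose is to detect a signal. Sections 6.5 and 10.1 list no safety or data monitoring committee, so the protocol names no independent body that would catch a misreading of the list.

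**Working it through.** **Inputs.** Prior Beta(0.5, 0.5) (Section 7.6.1). Planned sizes 20, 20, 20, 15, 15 and TV/LRV (Section 7.4). Stop limits s (Table 14): 1 for CRC and OvC, 5 for SCLC, 1 for TNBC and AML. Futility threshold 80% (Section 7.6.6).

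**Step 1: Stop limits.** With x responses in n patients the posterior is Beta(0.5 + x, 0.5 + n − x). P(ORR > TV) at the printed Stop limit, and at one response more, is 0.032 and 0.127 (CRC/OvC), 0.082 and 0.182 (SCLC), 0.037 and 0.147 (TNBC/AML). Against the 10% false-stop risk, the limits in Table 14 are correct.

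**Step 2: futility cut-offs.** Let k be the patients with known status, r the responses among them, and M the planned size. Future responses follow Y ~ BetaBinomial(M − k, 0.5 + r, 0.5 + k − r), and the predictive probability of Stop is P(Y ≤ s − r). For SCLC at 3 patients and no response:

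- all known: Y ~ BetaBinomial(17, 0.5, 3.5), P(Y ≤ 5) = 0.876
- one pending: Y ~ BetaBinomial(18, 0.5, 2.5), P(Y ≤ 5) = 0.793
- none assessed: Y ~ BetaBinomial(20, 0.5, 0.5), P(Y ≤ 5) = 0.355

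| Cohort | N / max responses | All N known | One pending |
|---|---|---|---|
| CRC/OvC | 8 / 0 | 0.835 | 0.798 |
| CRC/OvC | 18 / 1 | 0.852 | 0.781 |
| SCLC | 3 / 0 | 0.876 | 0.793 |
| SCLC | 7 / 1 | 0.832 | 0.752 |
| SCLC | 11 / 2 | 0.848 | 0.772 |
| SCLC | 14 / 3 | 0.824 | 0.731 |
| SCLC | 17 / 4 | 0.830 | 0.705 |
| TNBC/AML | 6 / 0 | 0.839 | 0.789 |
| TNBC/AML | 13 / 1 | 0.804 | 0.711 |

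The one-pending column is also the value at N − 1 known patients. So each printed cut-off is the smallest known N that reaches 80%: the list was computed on known outcomes. With none assessed, the first cut-offs carry 0.190 (CRC/OvC, 8 enrolled), 0.355 (SCLC, 3 enrolled) and 0.219 (TNBC/AML, 6 enrolled).

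**Step 3: how often the flag would appear.** The documents give no accrual rate, so this is a simulated range under assumptions: true ORR at TV, every response visible at Week 9, and one patient per 2, 4 or 6 weeks in the cohort. The stagger is taken as 7 weeks between the first three patients (first pembrolizumab at Week 6, plus one week). Each DLT gate makes patients 7 and 13 wait for Week 9 of patients 6 and 12 (Week 6 plus one 3-week cycle).

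| How the list is applied | OvC flagged | SCLC flagged |
|---|---|---|
| Intended: N = assessed patients | about 17–21% | about 31–34% |
| Enrolled N, checked as results arrive, stagger and gates in this cohort | about 25–29% | about 48–59% |
| Enrolled N, checked at each enrollment, stagger and gates in this cohort | 30–34% | 68–77% |
| Enrolled N, checked at each enrollment, no stagger or gates | 30–55% | 70–100% |

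With result-time checks there is no excess once the gap between patients exceeds 9 weeks: at 9.1 weeks the rates are about 20.5% (OvC) and 33% (SCLC).

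**The case against.** The strongest reply is that the criterion governs and the list only illustrates it. The Synopsis refers to evaluable patients. The lines below the first cut-offs speak of too little response data, so N was plainly meant to measure response data. Stopping is only to be considered, is non-binding, and is weighed with a full medical review. All of this is true. It limits the consequence, but it does not correct the printed definition: evaluable is undefined, Section 7.6.1 omits it, and the list is what the section offers as its stopping criteria. The mITT set is not linked to monitoring, and it rests on RECIST, which does not fit AML. Section 7.6.1 does count missing responses as non-responses, but for the primary analysis and not for monitoring.

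Three stronger inferences are tempting and are not supported:

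- **Any pending patient invalidates the flag.** This holds at the exact cut-offs only. Above them the criterion can be met with patients pending: SCLC with 6 enrolled, 3 assessed and no responses gives 0.876. Three of the nine one-pending values are also only just short (0.798, 0.793, 0.789).
- **SCLC would be flagged every time.** The 100% figure needs checks at each enrollment and the stagger and DLT gates to fall in other cohorts.
- **The boundaries or the Bayesian rule are wrong.** Both reproduce; only the meaning of N is at fault.

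**Conclusion.** Wrong as written, of minor to should-fix weight. The printed definition of N for CRC/OvC and SCLC, and its absence for TNBC/AML, conflicts with the section's own 80% criterion. The size at the cut-offs is exact and needs no accrual assumption: 0.804 to 0.876 with all outcomes known, 0.705 to 0.798 with one pending, and 0.190 to 0.355 at the first cut-offs with none assessed. The flag rates are illustrations that rest on the accrual, timing and response assumptions stated with them. For OvC with result-time checks the excess is modest. The documents do not show that a cohort would be closed wrongly: that would take a team that applies the list mechanically to an advisory flag.

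**What to change.** For all five cohorts in Section 7.6.6, replace the definition of N with: *N = patients in the cohort's primary efficacy analysis population whose response status for the primary endpoint is known; patients with a pending assessment are not counted.* Give evaluable the same meaning in the Synopsis, Section 7.6.1 and Section 7.6.6, including expanded cohorts.

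The sponsor should also state:

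- **When non-response counts as known, and whether a response must be confirmed.** Week 18 is one option, since both scans and AML marrow are scheduled then; it is not a requirement. It is also not exact, because early progressors enter N before late responders. With 0–50% of responders appearing late and 25–100% of non-responders determined early (assumptions), a Week 18 definition gives flag rates at TV of 9–25% (OvC) and 10–50% (SCLC).
- **The CRC population.** First reconcile Section 1.3.1.2.1 (MSS and MSI-H) with the Synopsis and Section 7.5 (MSS and MSI-L), then count N in that population. The Synopsis puts MSS at 80–90% of CRC. If all the rest were MSI-H and excluded (an assumption), 20 enrolled would give 20 × 0.8 = 16 to 20 × 0.9 = 18 countable patients. The CRC limits would then have to be computed for that number, or about 20/0.9 ≈ 22 to 20/0.8 = 25 patients enrolled to keep 20.

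Elsewhere the cut-offs stand as long as the planned 20 or 15 counts the same population. The cost is wording and a somewhat later futility call. At true ORR = LRV, a Week 18 definition adds on average about 0.5–2 (OvC) or 1–5 (SCLC) enrolled patients compared with a Week 9 definition.
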